Therefore, the objectives of the proposed study are (1) to close a gap in our knowledge⁴⁰ by assessing families' needs for support in a heterogeneous group of children with serious, advanced, ultra-rare diseases with and without comorbidities, who are unable to participate in shared medical decision-making; and (2) to test one such pACP intervention which may empower families by providing some control in a low control situation and increase families' capacity to participate in EOL decision making. The FAmily CEntered (FACE) pACP intervention, proven successful with cancer and HIV,⁵⁻¹² is adapted to children with ultra-rare diseases. Theoretically⁴¹⁻⁴⁴ informed and developed by the PI, **[name]**^{5,7} and Consultant, **[name]**,^{5,7} the proposed intervention will incorporate Respecting Choices Next Steps Pediatric ACP™ (RC), developed by [name] (unpublished) and Hammes. 45 specifically tailored for families whose child is unable to participate in health care decision-making. Our consultation with families of children with rare diseases and the National Organization for Rare Disorders (NORD) revealed that basic pPCEOL needs should be addressed first, prior to a pACP intervention. For the study to be able to meet families where they are, prior to randomization, all families will complete the Carer Support Needs Assessment Tool (CSNAT), ©46-51 adapted for use in pediatrics in our preliminary research through collaboration with NORD and affected families. In The CSNAT Approach, facilitators assess the prioritized pPCEOL needs and developed Shared Actions Plans for decision-making support. We propose pilot testing the three weekly sessions of FACE-Rare: CSNAT plus Respecting Choices, using a rigorous intent-to-treat, single-blinded, randomized controlled trial (RCT) design with 30 family/child dyads with 3-month post-intervention assessments. We will accomplish the objectives of this application by addressing the following specific aims:

AIM 1. To evaluate the initial efficacy of FACE-Rare in a pilot RCT on primary outcome: family quality of life (QoL) at 3-months post-intervention, controlling for co-variates (age, sex/gender, race of family caregiver) to seek an effect size for a future R01.

Hypotheses (H) 1a: FACE-Rare families will report significantly better QoL (emotional, spiritual) compared to controls.

H1b: Family caregiving appraisals will moderate effect of FACE-Rare on QoL outcomes.

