
B. Innovation B.1. Clinical Innovations. FACE-Rare offers (1) the opportunity to explore pACP, fora group not previously recognized in need of intervention; 126 (3) telemedicine to reach and follow-up families in ways not previously possible (see Resources); (4) a Community Advisory Board comprised of in part of fathers to increase male caregiver participation; (5) integration of caregiver illness representations, 42-44 with transactional stress and coping theory;^{44,61} and (6) respect for individual differences.¹²⁷ Findings may guide standard-of-care evidence-based practice¹²⁸ to overcome critical barriers^{129,130} to progress in palliative care for this "orphaned" group, meeting NIH's notice of interest addressing high-priority research in pediatric and end-of-life care. **B.2. Research Innovations.** This R21 refines previous research by using a rigorous intent-to-treat, single blinded, prospective RCT pilot design that enables us to (1) evaluate the initial efficacy of FACE-Rare; (2) examine outcomes that are measurable and valid across sex/gender and ethno-cultural perspectives; and (3) prevent bias by assuring Assessors are blind to random assignment. This R21 is consistent with NINR/NIH's Science of Caregiving (2017) noting the importance of caregiving across the lifespan. If the aims are achieved, a future R01 will use advanced statistical methods 131-136 and be informed by statistical advice from rare disease investigators, 136 enabling us to track changes in goals of care over time, i.e. "regoaling process." 137 C. Investigators. We have assembled an international, interdisciplinary team which includes nurse scientists and early stage investigators with a history of collaboration. The PI, [name], is a clinical psychologist with unique expertise in palliative care behavioral interventions with families. [name] is Director of the Myelin Disorders Program, a pediatrician, and an early stage investigator. [name] is Medical Director of the Complex Care Clinic, a pediatrician, and early-stage investigator. [name] is an internationally recognized palliative care pediatric nurse scientist. [name] contributes biostatistical expertise. [name] brings chaplaincy and ethics expertise. **[name]** is a nurse scientist from Respecting Choices. **[name]**, a Public Health Demographer and Palliative Care implementation expert in Australia, brings research expertise using CSNAT. **[name],** a physician and nurse, brings expertise on the science of measuring/interpreting religious data. D. Approach

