assent, the RA will conduct further screening for inclusion/exclusion criteria. *Baseline Visit:* At enrollment and prior to randomization, baseline measures in Table 3 will be obtained. Attendance will be recorded to assess effects of full vs. partial participation in FACE-Rare. *Follow-up Visit:* Blinded Assessor will obtain follow-up measures from families at 3-months post- intervention in person (clinic or home visit), by telephone or Telemedicine. See **Resources on Telemedicine**. **D.6.b. Measures**. Measures (**Table 2**) will be administered to the family by the blinded RA-Assessor. Investigators selected well-established measures with good reliability, validity, and normative data to increase replicability. Chart abstraction will be conducted by the blinded Assessor. A second blinded researcher will provide a validity *and* reliability check. Interrater reliability testing will be conducted. Rate differences will be reconciled by consensus, following well established procedures. ^{14,145} Disagreements will be resolved by the PI. See **Project Narrative** for questionnaire details.

Table 2: Measures	Method	Time	Description	
Primary Outcomes: *BL=Base	line *mo=mo	nth		
Beck Anxiety Inventory ¹⁴³	Survey	BL, 3 mo	QoL: emotional health. 21 items. Total Score will be used in analysis.	
FACIT-Spirituality-EX-Vs-4) ¹⁴⁴	Survey	BL, 3 mo	QoL : spiritual (meaning/purpose, peace). Is culturally sensitive to those with non-theistic beliefs. 23-items. Total Score will be used in analysis.	
Advance Care Document for Children with Rare Diseases ⁸⁴	Survey	3 mo	ACP Documentation in EHR & Decisional preferences- to continue all treatments; to continue all treatments with exceptions noted; to stop all treatments but comfort care.	
Standardized Data Abstraction Operationally defined ^{14,45,145} ,146	Chart Abstract	BL,3 mo or close-out	care prior to death, hospitalizations, Emergency Department visits, intensive care unit use,	
Moderators:				
Brief-Multidimensional Measure of Religion and Spirituality ^{62,63}	Survey	BL, 3 mo	Religious Coping : 5 items from our previous research: attend religious services, feel God's presence, pray privately, identify as religious, identify as spiritutal. 12,57,58	
Family Appraisal of Caregiving Questionnaire ¹⁴⁷	Survey	BL, 3 mo	Caregiver appraisal: caregiver strain, positive caregiving appraisals, caregiver distress, family well-being in past two weeks. 25 items.	
Time-Invariant Covariates:	•			

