In addition, if family consent is provided, Session 3 will be recorded by videotape or audiotape (family preference) and reviewed by the PI, [name] and [name], for implementation of quality control with regard to fidelity to the protocol, avoiding contamination of the control condition and monitoring for safety. Families who decline to be audiotaped or recorded by camcorder will still be included in the study, but their data will not be available for fidelity check. In our previous studies approximately 10% of participants declined to be audio or video taped.

This proposed project has chosen to utilize face-to-face data collection over audio computer-assisted self-interviews (ACSI). The rationale for this choice of data collection was based on sensitivity of the interview content, caregiver preference based on our pilot studies of families of children with rare diseases and feedback from the National Organization of Rare Diseases (NORD), and the potential for an improved risk assessment.

- a. Topic sensitivity: Due to the sensitivity of the topics discussed during the study interviews, we felt face-to-face conduct was preferable to ensure social respect to the study participants.
- b. Participant perception: Participants from our previous studies relayed a positive experience from the face-to-face assessments and interviews and viewed it as a caring experience, versus an impersonal means of data collection.

- c. Improved risk assessment: This technique will provide an additional way to protect the patients by providing study staff with the opportunity to directly observe emotional distress, or any additional risks, by using our standardized procedures described under **Adequacy of Protection Against Risks**.
- d. Increased engagement: This approach increased engagement with staff which in turn enhanced retention of participants in our previous studies.

We will defer the study visit if privacy cannot be maintained, unless participants agree to the study visit, despite the presence of other patients/family members. We will code for this in our data.

Potential Risks to Subjects

Potential risks associated with the study interviews include:

- 1) Emotional distress or family conflict related to discussion the death or dying of one's child.

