- 4) The PI will meet weekly with Children's National researchers to provide support to the research team and to address any emotional reactions or concerns they (RAs) have about a new family under consideration for recruitment and enrollment or issues that arose in the course of an intervention session;
- 5) We have a chaplain and an ethicist available for referral to discuss spiritual struggles or to help process conflicts about treatment preferences:
- 6) Procedures are clearly delineated about what the RAs should do if a participant should become suicidal or homicidal or psychotic during the intervention sessions or during any of the assessments; and
- 7) The Pl's available by cell phone. All research participants have a copy of the assent/consent form, which will contain appropriate Investigator phone numbers.

In addition to the procedures already in place, if they should prove to be insufficient, we also have an additional Co-I at Children's National, [name], who is an expert in safety issues in conducting research with dying children. [name] and [name] share an office suite at Children's National and have easy access to one another for consultations. [name], Co-Is and the Safety Monitoring Committee, as well as the study staff, will be responsible for ensuring that these procedures are followed and documented in the process notes and that the safety of participants is protected.

Although this study will be examining spirituality/religious experiences and beliefs, the FACE-Rare study is not a religious or spiritual intervention. We are including everyone regardless of religious affiliation. Instructions for responding to assessment measures include a statement that "Not all of these questions may apply to you. Please answer as best you can." Data on religious affiliation or no religious affiliation will be collected. If a participant gives no response, because it does not apply to him/her, the data will be coded as missing data.

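### Chart-abstraction disputes left after blinded consensus go to the PI, who probably knows the arm of most FACE-Rare families; the exposed tested outcome is mainly H3b

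*Combined protocol and SAP*

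**What the plan says.** Section B.2 presents assessor blinding as a strength of the design, meant to "prevent bias by assuring Assessors are blind to random assignment". The randomization and blindness text in D.3 conceals allocation from the Assessor and names chart abstraction among the tasks covered.

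Section D.6.b then describes four steps:

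1. "Chart abstraction will be conducted by the blinded Assessor".
2. "A second blinded researcher will provide a validity" and reliability check.
3. "Rate differences will be reconciled by consensus, following well established procedures".
4. "Disagreements will be resolved by the PI".

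Other places describe the PI's role:

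- The Specific Aims describe the intervention as "informed and developed by the PI" together with a consultant.
- Human Subjects section 1.b states that, with family consent, "Session 3 will be recorded by videotape or audiotape (family preference) and reviewed by the PI" and others, for fidelity and safety.
- Human Subjects section 2.b (further protections, item 4) has the PI meet the researchers weekly about families under consideration for enrolment "or issues that arose in the course of an intervention session".

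The consent and scheduling text in Human Subjects books Sessions 1 to 3 only for dyads randomized to the intervention. Controls receive treatment as usual.

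**The concern.** The plan takes care to keep two readers blind and then gives the last word to someone whose other duties reveal allocation and who has an intellectual stake in the intervention. Items that reach this step are those on which two blinded readers could not agree, so they are the ones most open to judgement.

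At stake is the blinded status of a secondary endpoint. H3b is tested with a two-sided Fisher's exact test on about 13 families per arm, where a single reclassified chart is a visible fraction of the data.

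**Working it through.** **Who knows what**

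| Person | Role for a disputed chart | Masking stated? | Route to allocation |
|---|---|---|---|
| Assessor | First abstractor | Yes (B.2, D.3, D.6.b) | See the objection on weekly meetings |
| Second researcher | Checks the abstraction | Yes (D.6.b) | None described |
| PI | Decides what consensus leaves open | No | Session 3 recordings; weekly talk about intervention sessions |

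Session 3 exists in one arm only, so a recording identifies its family as FACE-Rare. Human Subjects 1.b reports that about 10% declined taping in earlier studies. If that holds here, recordings would identify about 90% of FACE-Rare families who attend Session 3. The documents never state the PI's blinding status, so this is an inference from assigned duties. No text contradicts it.

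**Which outcomes are exposed**

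- *H3b* (document locatable in the record) needs a look at the chart. It is clearly exposed.
- *H3a* (document completed) is less clear. Table 2 gives the advance care document row the method Survey, although its description includes record documentation.
- *Utilization* is chart-abstracted, but D.9 reports it descriptively without a test.
- *Beck Anxiety Inventory and FACIT spirituality total* are self-reported and do not pass through this step.

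**How much one chart can do**

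The plan has no figure of its own to reproduce here. Inputs: 30 dyads and 15% attrition (D.9) give 30 × 0.85 = 25.5, stated there as 25 to 26, so I take 13 per arm. The 0.05 level is stated for model coefficients and assumed for Fisher's test. The counts are hypothetical.

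| FACE-Rare v control | p | One more FACE-Rare document | p |
|---|---|---|---|
| 6/13 v 1/13 | 0.073 | 7/13 v 1/13 | 0.030 |
| 7/13 v 2/13 | 0.097 | 8/13 v 2/13 | 0.041 |
| 8/13 v 3/13 | 0.111 | 9/13 v 3/13 | 0.047 |

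These pairs were chosen because they straddle 0.05. Large contrasts behave differently:

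- Section D.6 cites 0.84 v 0.029. Since 13 × 0.84 = 10.9 and 13 × 0.029 = 0.4, this is about 11/13 v 0/13, p=0.00002. Removing five FACE-Rare documents leaves 6/13 v 0/13, p=0.015.
- Section A.2.a cites 91% v 15%. Since 13 × 0.91 = 11.8 and 13 × 0.15 = 1.95, this is about 12/13 v 2/13, p=0.0002. Removing one leaves 11/13 v 2/13, p=0.001.

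**How often one chart would matter**

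Let p(t, c) be the two-sided Fisher p-value for t/13 v c/13. The chance that adding one FACE-Rare document crosses the threshold is the sum of Bin(t; 13, πF) × Bin(c; 13, πC) over all (t, c) with t + 1 > c, p(t, c) > 0.05 and p(t+1, c) ≤ 0.05.

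| πF v πC | Source | Probability |
|---|---|---|
| 0.84 v 0.029 | D.6 | 0.1% |
| 0.91 v 0.15 | A.2.a | 0.7% |
| 0.50 v 0.15 | Assumed moderate effect | 17% |

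Each figure supposes that exactly one chart is decided in favour of FACE-Rare. It is not the probability that such a dispute arises.

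**The case against.** The strongest case on the other side has five parts.

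1. **Few cases will reach the PI.** H3b asks whether a document can be found. Table 2 calls the abstraction standardized and operationally defined, and two blinded readers, reliability testing and consensus come first. This stands. The documents give no expected number of unresolved items, and it is probably small.
2. **The PI's unblinding is not stated.** A reader might infer that disputed outcomes are, as a matter of fact, decided unblinded. The documents do not go that far: they do not say in what form a disputed extract reaches the PI, and the manual of operating procedures is not in view. They support only that the PI probably knows the arm of most FACE-Rare families and that no masking is described.
3. **The effect may be too large for one chart to matter.** At the rates cited from earlier trials this is right. Those rates come from other populations, and D.6 itself anticipates contamination of controls, so a moderate difference cannot be excluded.
4. **Weekly meetings prove too much.** D.7.b lists the RA-Assessor as attending the PI's weekly meeting. If session discussion there unblinds the PI, it may unblind the Assessor too. That is fair, so the argument rests mainly on the recordings.
5. **Masking may be unattainable.** The section on breaches of confidentiality says the original signed Session 3 plan goes into the child's record, so the chart itself may reveal the arm to any reader. This limits what a new adjudicator can achieve. It does not justify giving the decision to someone who probably knows the arm already.

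**Conclusion.** The point holds in limited form. The tie-break in D.6.b is inconsistent with the blinded chart abstraction that B.2, D.3 and D.6.b itself promise, because the final decider co-developed the intervention and reviews recordings made in one arm only.

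The exposure is mainly H3b. A reader might extend it to both H3 outcomes and to the utilization results. Table 2 leaves it unclear how far H3a depends on the chart, and utilization carries no test, so only its reported counts could shift.

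The size is modest. One chart could move a borderline H3b result across 0.05 if the true difference is moderate, but almost never if it resembles the earlier trials. This rests on 13 per arm, a two-sided 0.05 level for Fisher's test, hypothetical counts, and an unknown but probably small number of disputes. Nothing here threatens the self-reported quality-of-life outcomes or the validity of the trial. The change is worth making because it is cheap and closes a gap in a safeguard the plan advertises.

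**What to change.** In D.6.b, replace the sentence that gives disagreements to the PI. Differences left after consensus should go to an existing co-investigator who takes no part in intervention delivery, recording review or session discussions, and who receives the disputed extract without an arm label as far as the chart content allows. Report the number of adjudicated items by arm.

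Do not instead count a document only when both abstractors find it. A document that one reader finds is locatable, so such a rule would redefine H3b and turn abstractor error into outcome failure, mostly in the arm with more documents.

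The cost is one sentence and a few charts of a co-investigator's time. Roles are redacted, so the study team must confirm that a suitable unexposed person exists. Masking may remain imperfect because the Session 3 plan is filed in the record.

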
facilitator will notify intervention or control families the day of random assignment and schedule the approximately weekly study visits for those randomized to FACE-Rare and assessments for those randomized to control. Allocation will be concealed from the Assessor to prevent bias during the administration of outcome questionnaires, process measures, and chart abstraction. **D.4. Retention and Attrition.** Investigators will use proven procedures for retention.⁴ Investigators have a +/- one-month window for completion of 3-month post-intervention assessments to meet family needs. Using such procedures, only 5%⁹-7%⁶ attrition was documented from earlier trials at 3-months post-intervention.^{56,57} Use of TAU in FACE-TC trials did not result in significant differential attrition over time by study arm.^{6,106} Weekly staff meetings will identify retention problems early. Monthly conference calls with investigators and the Community Advisory Board will rectify them. Telemedicine should mitigate transportation/child-care/immune compromise barriers (e.g. avoid hospital during flu season). Thus, investigators conservatively estimate 15% attrition.

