Demographic Questionnaire	Survey	BL	Age, sex/gender, race, ethnicity of family caregiver and child. Child technology dependent. Education, household income, marital status, employment.	
Process Measures:				
Satisfaction Questionnaire ^{7,56}	Survey	Visit 4	Study specific process measure to assess adverse events and benefit/burden of participation 12 items.	
Quality of Communication Survey Visit 4 Questionnaire 182		Visit 4	Study specific process measure to assess how participating families perceived the interviewer's quality of communication and rate the overall quality of discussion. 5 items. Adapted from Curtis et al. 182	
Role stress ¹⁴⁸	Survey	Visits BL, 3 mo	Visual analogue scale 0-100. "How stressful is it for you to make medical decisions for your child?" 1 item.	

including scientific and clinical leadership. [name] will also have primary responsibility for practical issues in training and implementation. [name], will provide oversight of logistics necessary to conduct the study, regulatory oversight, data collection, and management. Children's National is the data coordinating center. See Overall Structure of Study Team. D.7.a. Site Initiation. To begin screening/enrollment (1) all personnel are certified in Human Subjects Research training; (2) personnel are recruited and trained for their roles. [name] and [name] will verify all components in place for the logistics of screening, enrolling, scheduling, performing assessments, administering interventions, and collecting the data. Training and competency criteria will be used to ensure fidelity to the protocol. A manual of operating procedures will be created. D.7.b.

Communication. The PI is responsible for facilitating all communications and will meet weekly, face-to-face, with the research team (RA-Interventionist, RA-Assessor, [name]). Monthly conference calls will be had with PI, Co-Is, and consultants. [name] and [name] will supervise Respecting Choices Facilitator monthly through conference calls. Identified barriers will be addressed and appropriate action taken. Meeting minutes/benchmarks will be kept by [name] and circulated.

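### The weekly team meeting, as written, can reveal a family's arm to the blinded Assessor before the 3-month interview

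*Combined protocol and SAP*

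**What the plan says.** Three parts of the combined protocol and SAP describe weekly meetings.

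- **D.7.b Communication** gives the attendees: "The PI is responsible for facilitating all communications and will meet weekly, face-to-face, with the research team (RA-Interventionist, RA-Assessor, [name". It adds: "Meeting minutes/benchmarks will be kept by [name] and circulated". It does not say who receives the minutes.
- **Protection Against Risks, further protections, item 4** gives a purpose: "The PI will meet weekly with Children's National researchers to provide support to the research team". The content is the emotional reactions or concerns that research assistants "have about a new family under consideration for recruitment and enrollment or issues that arose in the course of an intervention session".
- **D.4 Retention and Attrition** adds: "Weekly staff meetings will identify retention problems early".

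On blinding, D.3 (Randomization and Blindness) states: "Allocation will be concealed from the Assessor to prevent bias during the administration of outcome questionnaires, process measures, and chart abstraction". The section on informed consent and waiver of assent repeats that the RA-Assessor is not told the randomization result, and B.2 lists Assessor blinding among the trial's protections against bias.

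D.3 also shows how the arms differ in contact. After randomization the facilitator is to "schedule the approximately weekly study visits for those randomized to FACE-Rare and assessments for those randomized to control".

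**The concern.** The person who must not know allocation is scheduled to sit each week with the person who delivers the intervention, in a meeting whose stated content includes what happened in intervention sessions. Control families have no such sessions. Discussing a session with the family identified therefore discloses that family's arm.

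The Assessor's blind carries much of the weight in this design. Caregivers know their arm. The QoL outcomes under Aim 1 are self-reports (Beck Anxiety Inventory and FACIT-Spirituality). The Human Subjects section has questionnaires read to all caregivers and prefers face-to-face collection, so the interviewer's manner could influence answers. The same Assessor administers every 3-month assessment and abstracts the chart. The pilot's declared product is an effect size for a future R01, and an interviewer effect would be carried into it.

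**Working it through.** The plan gives no figure to reproduce on this point. The check is a comparison of the relevant sections.

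1. **Does the Assessor attend?** Yes. D.7.b names the RA-Assessor and the RA-Interventionist as attendees of the same weekly meeting with the PI.

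2. **Is session content discussed at that meeting?** Item 4 describes a weekly meeting led by the PI with the research team. D.6 defines that team as the blinded RA-Assessor, the CSNAT interventionist and the Respecting Choices interventionist. D.7.b uses the same term. D.1 describes a single site; parts of the Human Subjects section speak of several sites, but item 4 refers to the Children's National researchers in particular. One meeting is the natural reading, though it is not stated. If there are two, nothing excuses the Assessor from either.

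3. **Does the discussion reveal arm?** This depends on the topic.

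| Topic | Source | Families who can be named | Reveals arm? |
|---|---|---|---|
| Issues from an intervention session | Item 4 | FACE-Rare only | Yes, if the family is identifiable |
| Retention problems | D.4 | Either arm | Only if the details point to sessions |
| New family considered for enrollment | Item 4 | Not yet randomized | No |

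4. **Is it before outcome collection?** Yes. Assume three sessions one week apart (two weeks from first to last), 13 weeks for three months, and about 4 weeks either way for the one-month window in D.4. From first session to interview is then 2 + 13 = 15 weeks, with a range of 15 − 4 = 11 to 15 + 4 = 19. About 11 to 19 weekly meetings fall in that interval. This counts opportunities, not disclosures.

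5. **Is there a safeguard?** D.3 and the consent section state the rule but give no procedure for the meeting. The documents contain no split agenda, no bar on identifying families, no restriction on minutes and no check for unblinding. D.7.a says that a manual of operating procedures will be written but describes no such content.

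**The case against.** The strongest reply is that the concealment rule governs all staff conduct, meetings included, and that agendas belong in the manual of operating procedures, which is not among the documents. The absence of a safeguard in the protocol does not prove its absence in practice. This stands, and it limits the claim to what can happen. It does not remove the point: the protocol itself prescribes joint attendance and session discussion, so a general rule elsewhere leaves a conflict in the text.

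Three stronger readings are tempting and are not supported.

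- **That blinding fails by routine.** Item 4 describes discussion by exception, of concerns and issues that arose. It does not call for review of every session, and it does not say that families are identified.
- **That all 15 FACE-Rare families become known, and the 15 controls by elimination.** Control families can be raised for retention and unrandomized families for recruitment. Elimination would work only if every FACE-Rare family were identified through a session.
- **That the false-positive rate is materially inflated.** The documents give no bias size. Suppose a shift of 0.1 to 0.3 SD in every FACE-Rare family. With 26 dyads retained (13 per arm), the standard error of the standardized difference is √(2/13) = 0.39, and a two-sided 5% t-test with 24 degrees of freedom rejects 5.7% to 11.4% of the time under no true effect. If half the families are disclosed, the mean shift is 0.05 to 0.15 SD and the range is 5.2% to 6.6%. The result follows the assumptions, so none of these figures is a finding.

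It is also fair to say that other routes to unblinding remain. Caregivers know their arm, and the Session 3 advance care plan goes into the chart that the Assessor abstracts. Splitting the meeting will not by itself secure the blind. That is no reason to leave an avoidable route open.

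**Conclusion.** The concern holds in a limited form. The meeting arrangements in D.7.b and item 4 can disclose to the Assessor that a family is in FACE-Rare, before that family's 3-month interview and contrary to B.2, D.3 and the consent section. The conclusion rests on reading D.7.b and item 4 as one meeting, or at least on the Assessor not being excused from the second, and on families being identifiable when sessions are discussed.

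The number of families affected and the size of any bias cannot be derived from the documents. Whatever interviewer bias arose would carry into the estimated effect size, which matters more in this pilot than any single significance test. The change is justified because the conflict is in the written procedure and costs little to remove. It does not need proof that unblinding will occur.

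**What to change.** Amend D.7.b and item 4 of the further protections as follows.

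- The RA-Assessor attends only an arm-neutral part of the weekly meeting: accrual, scheduling by study ID, and data queries.
- Intervention-session content, and any retention discussion that would reveal arm, is held without the Assessor. The second blinded abstractor in D.6.b is also excluded, if that person attends at all.
- Minutes of that part are not circulated to blinded staff.

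As a useful addition, record the Assessor's guess of allocation after each 3-month interview, so that the success of blinding can be reported.

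The cost is an agenda rule, mirrored in the manual of operating procedures, and a separate debrief for the Assessor on distress seen at assessments. The advance care plan in the abstracted chart, and disclosure by caregivers, need separate handling.
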